8.9 Precautions and Restrictions

An interference with serological testing has been described with the anti-CD38 antibody daratumumab. Daratumumab binds to CD38 on RBCs and results in a positive indirect antiglobulin test (indirect Coombs test). A daratumumab-mediated positive indirect antiglobulin test may persist for up to 6 months after the last daratumumab infusion. Daratumumab bound to RBCs masks detection of antibodies to minor antigens in the patient's serum. The determination of a patient's ABO and Rh blood type are not affected. Type and screen patients before starting modakafusp alfa if this was not performed previously.

Patients should not drive, operate dangerous tools or machinery, or engage in any other potentially hazardous activity that requires full alertness and coordination if they experience sedation while enrolled in this study.

Patients are to be instructed to limit the use of alcohol while enrolled in this study.

8.9.1 Contraception and Pregnancy Avoidance Procedures

It is not known what effects modakafusp alfa has on human pregnancy or development of the embryo or fetus; therefore, patients participating in this study should avoid becoming pregnant or impregnating a partner. Patients of reproductive potential should use effective methods of contraception through defined periods during and after study treatment as specified below. Patients must also adhere to any applicable local (country-specified) treatment-specific pregnancy prevention guidelines.

Reproductively female patients must meet one of the following:

- Postmenopausal for at least 2 years before the screening visit OR
- Surgically sterile, OR
- If they are of childbearing potential (as defined in Section 9.3.9), due to unknown risks and potential harm to an unborn child/infant, must agree to the following:
 - Agree to practice 1 highly effective method of contraception and 1 additional effective (barrier) method at the same time (Table 8.d) from the time of signing the informed consent

through 7 days after the last dose of modakafusp alfa or 4 months after the last dose of pembrolizumab, whichever is longer OR

- Agree to practice true abstinence, when this is in line with the preferred and usual lifestyle of the subject. (Periodic abstinence [eg, calendar, ovulation, symptothermal, postovulation methods], withdrawal, spermicides only, and lactational amenorrhea are not acceptable methods of contraception. Female and male condoms should not be used together.)
- Agree not to donate an egg or eggs (ova) or breastfeed a baby during the study through 7 days after the last dose of modakafusp alfa or 4 months after the last dose of pembrolizumab, whichever is longer.

Reproductively male patients, even if surgically sterilized (ie, status postvasectomy), must agree to one of the following:

- Agree to practice effective barrier contraception ([Table 8.d](#)) during the entire study treatment period and through 7 days after the last dose of modakafusp alfa (no restriction for pembrolizumab) OR
- Agree to practice true abstinence, when this is in line with the preferred and usual lifestyle of the subject. (Periodic abstinence [eg, calendar, ovulation, symptothermal, and postovulation methods], withdrawal, spermicides only, and lactational amenorrhea are not acceptable methods of contraception. Female and male condoms should not be used together.)
- Agree not to donate sperm during the study and for 7 days after the last dose of modakafusp alfa (no restriction for pembrolizumab).

Table 8.d Highly Effective Methods of Contraception

Highly Effective Methods	Additional Effective (Barrier) Methods
Combined (estrogen and progestogen containing) hormonal contraception associated with inhibition of ovulation	
Oral	
Intravaginal	
Transdermal	Male or female condom with or without spermicide (female and male condoms should not be used together)
Progestogen-only hormonal contraception associated with inhibition of ovulation	
Oral	
Injectable	
Implantable	
Intrauterine device	
Intrauterine hormone-releasing system	
Bilateral tubal occlusion	Cap, diaphragm, or sponge with spermicide
Vasectomized partner	
Sexual abstinence	

8.10 Management of Specific Adverse Reactions

8.10.1 Infusion-Related Reactions

An IRR can develop during or shortly after administration of a drug. Signs and symptoms may include pruritus, urticaria, fever, rigors/chills, diaphoresis, bronchospasms, and cardiovascular collapse. In modakafusp alfa studies, IRRs are designated as AESIs.

Premedication is detailed in Section 8.8.1. Patients should be carefully monitored during modakafusp alfa infusions. Trained trial staff at the clinic should be prepared to intervene in case of any IRRs and resources necessary for resuscitation (eg, agents such as epinephrine and aerosolized bronchodilators; also, medical equipment such as oxygen tanks, tracheostomy equipment, and a defibrillator) must be available at bedside.

Patients will be advised to promptly report signs and symptoms that may indicate IRRs, including fever, chills, dizziness, nausea, vomiting, flushing, cough, headache, and rash during or soon after end of infusion.

Post-medication may be considered at the investigator's discretion, as medically indicated, and per Section 8.8.2.

In case of an infusion reaction, serum samples should be taken for central evaluation of immunogenicity and circulating biomarkers (Appendix A). These blood draws must not interfere with patient care and blood tests necessary for the acute care of the patient.

All AESIs will be reported to Takeda Global Pharmacovigilance in an expedited manner irrespective of the event's seriousness or causal relationship as described in Section 10.2.1. When recording IRRs in the eCRF, the signs and symptoms should be recorded and should be marked as an AESI.

8.10.1.1 IRRs After Modakafusp Alfa Dosing

The recommendations for managing IRRs related to modakafusp alfa are presented in Table 8.e and Table 8.f.

Table 8.e Recommendations for Managing Grade 1 and Grade 2 IRRs

IRR	Action
Grade 1 or 2	The infusion should be paused. When the patient's condition is stable, infusion may be restarted at the investigator's discretion. Upon restart, the infusion rate should be half of that used before the interruption. Subsequently, the infusion rate may be increased at the investigator's discretion. Consider pre- and postmedication before restarting the infusion and for future modakafusp alfa administrations.
Grade 2 event of laryngeal edema, or Grade 2 event of bronchospasm that does not respond to systemic therapy.	Patient must be withdrawn from treatment if the event does not resolve within 6 hours from onset.

Table 8.f Recommendations for Managing Grade ≥ 3 IRRs

IRR	Action
Any Grade 4 life-threatening event:	Patient must be withdrawn from treatment.
Grade 3 bronchospasm or laryngeal edema:	Patient must be withdrawn from treatment.
Grade 3 events other than bronchospasm or laryngeal edema:	Infusion must be stopped, and the patient must be observed carefully until resolution of the IRR.
If the intensity of the IRR remains at Grade 3 after 2 hours:	Patient must be withdrawn from treatment.
If the intensity of the IRR decreases to Grades 1 or 2:	Infusion may be restarted at the investigator's discretion. Administer corticosteroids, acetaminophen, and antihistamines per Sections 8.8.1 and 8.8.2 before restarting infusion. Within 2 hours upon restart, the infusion rate should be half of that employed before the interruption. Subsequently, the infusion rate may be increased at the investigator's discretion.
If the intensity of the IRR returns to Grade 3:	The procedure described above may be repeated after restart of the infusion at the investigator's discretion.
If the intensity of the IRR increases to Grade 3 for a third time:	Patient must be withdrawn from treatment.

IRR: infusion-related reaction.

8.10.1.2 *IRRs After Pembrolizumab Dosing*

Patients with Grade 1 or 2 infusion reaction may continue to receive pembrolizumab with close monitoring. For Grade 3 or 4 infusion reactions, infusion should be stopped and pembrolizumab permanently discontinued.

8.10.2 **Low Platelet Counts**

Treatment decisions will be based on a patient's platelet counts assessed before any transfusion. Low platelet counts (Grade 4) should cause scheduled infusions to be postponed or to be permanently discontinued. If at any time the platelet count is less than $10 \times 10^9/L$, or if the patient shows a bleeding tendency considered to be due to thrombocytopenia occurring after initiation of modakafusp alfa treatment, the patient should be withdrawn from modakafusp alfa treatment unless clinical benefit is observed and the investigator considers that thrombocytopenia can be managed with dose modifications. The investigator can consider the usage of corticosteroids, IVIG or thrombopoietin agonists in selected cases depending on severity, duration, transfusion requirements, and additional risk factors for bleeding and based on the suspected underlying mechanism. Platelet transfusion and close monitoring of platelet counts should follow institutional guidelines.

8.10.3 **Management of Immune-Mediated Adverse Events**

Pembrolizumab can cause pneumonitis, colitis, hepatitis, endocrinopathies, nephritis, skin adverse reactions, IRRs, and other immune-mediated AEs. Monitoring of these AEs is required in both the safety lead-in and expansion cohorts in the combination arm. Patients with AEs that are suspected to be related to pembrolizumab should be evaluated by appropriate methods, including physical examinations, laboratory tests, and imaging. These irAEs will be treated based on standard of care, local institutional guidance, the WARNINGS AND PRECAUTIONS section of the package insert, and the proper use guidance of pembrolizumab. It is recommended that the management of irAEs follow NCCN ([NCCN 2021](#)) or SITC ([Puzanov et al. 2017](#)) guidance.

8.11 **Blinding and Unblinding**

This is an open-label study.

8.12 **Description of Investigational Agents**

Modakafusp alfa is a humanized anti-CD38, IgG4, mAb fused to an attenuated IFN- α 2b. The initial frozen liquid modakafusp alfa formulation is used for all phase 1b dose escalation patients. The redeveloped lyophilized modakafusp alfa formulation is to be used in dosing phase 2 patients. Additional details can be found in the modakafusp alfa IB.

Pembrolizumab solution for infusion consists of 100 mg/4 mL (25 mg/mL) in a single-dose vial or powder for solution for infusion 50 mg (1 vial contains 50 mg pembrolizumab). Please refer to the pharmacy manual and the most recent pembrolizumab SmPC for details.

8.13 Preparation, Reconstitution, and Dispensation

Parenteral drug products should be inspected visually for particulate matter and discoloration before administration, whenever the solution and container permit.

8.13.1 Modakafusp Alfa

Modakafusp alfa is an anticancer drug; as with other potentially toxic compounds, caution should be exercised when handling modakafusp alfa. Detailed information is available in the IB and pharmacy manual.

8.13.2 Pembrolizumab

Please refer to the most recent SmPC for preparation, reconstitution, and administration instructions.

A commercially available IV formulation of pembrolizumab background therapy will be used. In countries or study centers where pembrolizumab is designated a noninvestigational product, sites will be expected to source this commercially available product through their local hospital pharmacy or licensed distributor. In countries or centers where pembrolizumab is designated as an investigational product, sites will have pembrolizumab supplied and packaged by the sponsor. This supply will be labeled appropriately for investigational use as per the regulations of the relevant country health authority.

8.14 Packaging and Labeling

Supplies of modakafusp alfa and pembrolizumab will be labeled according to the current ICH guidelines on GCP and Good Manufacturing Practice and will include any locally required statements.

8.15 Storage, Handling, and Accountability

8.15.1 Modakafusp Alfa

The investigator or designee must confirm that appropriate temperature conditions have been maintained for all modakafusp alfa received and that any discrepancies are reported and resolved before use of modakafusp alfa.

Temperature conditions for modakafusp alfa, a list of ancillary supplies approved for use with modakafusp alfa, and thawing or reconstitution and dilution procedures for modakafusp alfa vials are provided in the pharmacy manual.

Each modakafusp alfa shipment will include a packing slip listing the contents of the shipment, and any applicable forms.

The investigator is responsible for ensuring that deliveries of modakafusp alfa and other study materials from the sponsor are correctly received, recorded, and handled, and stored safely and properly in accordance with the Code of Federal Regulations (CFR) or national and local regulations, and used in accordance with this protocol.

Only patients enrolled in the study may receive modakafusp alfa, and only authorized staff at the investigational center may supply or administer modakafusp alfa. All modakafusp alfa must be stored in a secure, environmentally controlled, and monitored (manual or automated) area in accordance with the labeled storage conditions or appropriate instructions with access limited to the investigator and authorized staff at the investigational center.

The investigator, institution, or head of the medical institution (where applicable) is responsible for modakafusp alfa accountability, reconciliation, and record maintenance (eg, receipt, reconciliation, and final disposition records).

A record of modakafusp alfa accountability (modakafusp alfa and other study materials received, used, retained, returned, or destroyed) must be prepared and signed by the principal investigator or designee, with an account given for any discrepancies. Empty, partially used, and unused modakafusp alfa will be disposed of, retained, or returned to the sponsor or designee.

Further guidance and information are provided in the pharmacy manual.

8.15.2 Pembrolizumab

Pembrolizumab must be stored in a secure, limited-access location, according to conditions specified on the drug label. The investigator or designee must confirm that appropriate temperature conditions have been maintained and that any discrepancies are reported and resolved before use. Refer to the pharmacy manual and/or the most recent SmPC for additional details.

9.0 STUDY CONDUCT

This trial will be conducted in compliance with the protocol, GCP, applicable regulatory requirements, and ICH guidelines.

9.1 Study Personnel and Organizations

The contact information for the project clinician for this study, the central laboratory and any additional clinical laboratories, the coordinating investigator for each member state/country, and the contract research organization (CRO) team may be found in the Study Manual. A full list of investigators is available in the sponsor's investigator database.

9.2 Arrangements for Recruitment of Patients

Recruitment and enrollment strategies for this study may include recruitment from the investigator's local practice or referrals from other physicians. If advertisements become part of the recruitment strategy, they will be reviewed by the internal review board (IRB)/independent ethics committee (IEC).

9.3 Study Procedures

Sites will make every effort to see patients in the clinic to complete all study-specified assessments as outlined in the SOE ([Appendix A](#)). In unavoidable circumstances, such as the COVID-19 public health emergency, exceptions can be made for alternative methods for conducting patient visits

and performing laboratory and imaging assessments as detailed below. Remote visits and telemedicine must comply with national and local laws and regulations. Such instances will be documented in the study records and electronic case report form (eCRF) if applicable, and the sponsor will be informed.

Refer to the SOE ([Appendix A](#)) for timing of assessments. Additional details are provided as necessary in the sections that follow. Evaluations during the screening period are to be conducted within 21 days before administration of the first dose of the study drug. Some procedures conducted during the screening period that are performed within 4 days of C1D1 may also be used as the predose evaluation and do not need to be repeated, unless otherwise specified.

9.3.1 Informed Consent

Each patient must provide written informed consent before any study-required procedures are conducted, unless those procedures are performed as part of the patient's standard care.

If necessary, informed consent may be obtained from a potential or current trial participant via electronic informed consent capabilities or an electronic face-to-face consent interview when these individuals are unable to travel to the site.

9.3.2 Patient Demographics

The date of birth, race, ethnicity, and sex of the patient are to be recorded during screening.

9.3.3 Medical History

During the screening period, a complete medical history will be compiled for each patient. The history will emphasize the background and progress of the patient's malignancy and include a description of prior therapies for it and the best response achieved by each one. Available key pathology and genomic biomarkers previously obtained from patient's tumor should be collected. In the phase 2 expansion, a patient's history of IRR to prior CPI therapy will be collected.

In addition, concomitant medications will be recorded as specified in [Section 9.3.10](#).

The most recent prescreening diagnostic-quality computed tomography (CT) and/or magnetic resonance imaging (MRI) scans acquired for disease assessment, if available, should be submitted to the imaging core laboratory vendor for storage and for potential retrospective central reading. (refer to [Section 9.3.14.2](#)). The date of the scan(s) should be indicated. Availability of prescreening scan(s) is not a prerequisite for study eligibility.

9.3.4 Physical Examination

A physical examination will be performed (complete or symptom-directed) per standard of care at the times specified in the Schedule of Events ([Appendix A](#)).

If an investigator considers it safe and appropriate for a subject to miss a protocol-specified physical examination for COVID-19-related reasons, the study site physician or other qualified site staff will speak directly with the subject by telephone or other medium (eg, a computer-based video communication) to assess subject safety and overall clinical status with a plan for in-person

evaluation if signs and symptoms warrant. Such instances will be documented in the study records and electronic case report form (eCRF) if applicable, and the sponsor will be informed.

9.3.5 Patient Height

Patient height will be measured during the screening visit only.

9.3.6 Patient Weight

Patient weight will be measured at the times specified in [Appendix A](#). Initial dose should only be adjusted for a $\geq 10\%$ change in body weight (Section 8.1).

9.3.7 Vital Signs

Vital signs include temperature, pulse, respiratory rate, and oxygen saturation. They include also supine, semirecumbent, or seated measurements of diastolic and systolic blood pressure (after 3 to 5 minutes in this position; all subsequent measurements should be performed in the same initial position). Vital signs will be measured at the times specified in [Appendix A](#).

Blood pressure will be measured every 30 minutes (± 5 minutes) during the first 4 infusions, after the end of the infusion, and at any moment if the patient complains of symptoms consistent with IRR. If the patient experiences hypotension (with or without symptoms) intensive blood pressure monitoring according to local practice should be instituted. The patient cannot be released from the site until blood pressure has returned to Grade 1 or baseline for at least 1 hour.

Any vital sign value that is judged by the investigator as clinically significant will be recorded both in the source documentation and the eCRF as an AE and monitored as described in Section 10.2.

9.3.8 ECOG Performance Status

ECOG performance status ([Oken et al. 1982](#)) will be evaluated at the times specified in [Appendix A](#).

9.3.9 Pregnancy Testing

Pregnancy tests will be measured at the times specified in [Appendix A](#). A serum or urine pregnancy test will be performed for patients of childbearing potential with negative results during screening, and again at C1D1 (baseline) if the screening test was performed more than 72 hours before the C1D1 dosing. A serum or urine pregnancy test must be performed predose (within 72 hours prior to dosing) on Day 1 of each cycle with negative results available before modakafusp alfa is administered. A serum or urine pregnancy test is required at EOT.

A patient of childbearing potential is defined as a patient with a uterus/ovary(ies) who (1) has not undergone a hysterectomy or bilateral oophorectomy or (2) has not been naturally postmenopausal (amenorrhea following cancer therapy does not rule out childbearing potential) for at least 24 consecutive months (ie, has had menses any time in the preceding 24 consecutive months).

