4.3.4 Potential Effects of Pembrolizumab

Pembrolizumab toxicities are generally associated with the activation of autoreactive T-cells resulting in immune-related adverse events (irAEs) and embryofetal toxicity. The safety of pembrolizumab at 200 mg every 3 weeks or 400 mg every 6 weeks has been evaluated in multiple clinical studies, and the most common adverse drug reactions (ADRs) ($\geq 20\%$) were fatigue, diarrhea, and nausea. The majority of ADRs reported were of Grade 1 or 2 in severity. For detailed information regarding the safety of pembrolizumab administration please refer to the Food and Drug Administration (FDA)-approved package insert ([Keytruda \(pembrolizumab\) PI 2018](#)).

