8.0 STUDY DRUG

8.1 Study Drug Administration

All protocol-specific criteria for administration of study drug must be met and documented before drug administration. Study drug will be administered only to eligible patients under the supervision of the investigator or identified subinvestigator(s).

The initial dose should be based on a patient's weight at screening and only adjusted if there is a $\geq 10\%$ change in body weight.

Investigational sites should refer to the pharmacy manual for preparation of each dose. Modakafusp alfa doses < 1.5 mg/kg will be administered over 1 hour (± 10 minutes). Modakafusp alfa doses ≥ 1.5 mg/kg will be administered over 2 hours (± 10 minutes) and could be extended to 4 hours at the investigator's discretion. Any decrease in infusion duration must be discussed with and agreed upon by the sponsor. If a patient presents with an infusion-related reaction at any dose level, the duration of the infusion may be extended per investigator's discretion. Total time from modakafusp alfa dosing solution preparation until end of infusion must not exceed 7 hours.

In the combination treatment cohorts, the recommended pembrolizumab dose of 400 mg will be administered as an IV infusion over 30 ± 10 minutes Q6W in combination with modakafusp alfa. Please see premedication and observation guidelines in Section 8.8.1.

Pembrolizumab will be administered before modakafusp alfa on days when both modakafusp alfa and pembrolizumab are given. At least 30 minutes should elapse between the completion of the infusion of the first study drug and the initiation of the infusion of the second study drug.

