8.6.4 Criteria for Discontinuing of Treatment with Study Drugs

Patients should discontinue treatment with either modakafusp alfa or pembrolizumab, or both, if they meet any of the criteria listed below. Patients who discontinue pembrolizumab for reasons other than irAEs may continue modakafusp alfa treatment as a single agent if modakafusp alfa discontinuation criteria are not met; patients who discontinue modakafusp alfa may continue pembrolizumab as a single agent if pembrolizumab discontinuation criteria are not met. In the event of discontinuation of study therapy (modakafusp alfa and pembrolizumab), patients will undergo the end of treatment (EOT) visit.

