10.4 Procedures for Reporting Drug Exposure During Pregnancy and Birth Events

Any participant who is found to be pregnant during the study should be withdrawn and modakafusp alfa, and pembrolizumab if applicable, immediately discontinued. In addition, any pregnancies in the partner of a study participant during the study should also be recorded, after authorization from the study participant's partner.

If a participant or a study participant's partner agrees to their primary care physician being informed, the investigator should notify the primary care physician that the participant was participating in a clinical study at the time of the pregnancy and provide details of the study drug the subject received.

All pregnancies, including those in partners of study participants, will be followed to final outcome using the pregnancy form. The outcome, including any premature termination, must be reported to the sponsor. An evaluation after the birth of the child will also be conducted.

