- ^c Vital signs will be measured before starting the infusion and after the completion of the infusion. Vital signs include temperature, pulse, respiratory rate, oxygen saturation, and blood pressure. Blood pressure will be measured every 30 minutes (± 5 minutes) during the first 4 infusions, after the end of the infusion, and at any moment if the patient complains of symptoms consistent with an IRR. If the patient experiences hypotension (with or without symptoms), intensive blood pressure monitoring according to local practice should be instituted. The patient cannot be released from the site until blood pressure has returned to Grade 1 or baseline for at least 1 hour. During the first infusion and for 6 hours postinfusion in the first 2 treatment cycles, patients should be continually monitored by medically qualified staff with access to emergency medical equipment and medications to manage IRRs. In Cycle 3 and beyond, patients should be continually monitored for at least 2 hours before the end of infusion, and the monitoring duration could be extended per a patient’s prior dosing experience.
- ^d In case of an IRR, blood draws should be performed for central evaluation of cytokines, chemokines, complement, immune complex formation and ADAs. The following samples should be collected: serum sample for circulating biomarkers and serum sample for immunogenicity.
- ^e The recommended pembrolizumab dose of 400 mg will be administered as an IV infusion over 30 ± 10 minutes Q6W. Pembrolizumab will be administered before modakafusp alfa on days when both modakafusp alfa and pembrolizumab are given. At least 30 minutes should elapse between the completion of the infusion of the pembrolizumab and the infusion of modakafusp alfa.

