72 h after end of infusion (±2 h)							X1					X1		

CxDx: Cycle x Day x; D: Day; ECG: electrocardiogram; h: hour(s); min: minute(s); PK: pharmacokinetic(s).

CONFIDENTIAL

When the timing of a PK or safety laboratory blood sample coincides with the timing of ECG measurements, the ECG will be completed before the collection of the blood sample. The triplicate ECG measurements should be completed immediately before the corresponding PK blood draw.

- ^a Timing of the morning visits should occur at approximately the same time as the morning dosing times on previous days of the cycle. The date/time of the start and end of infusions should be recorded accurately. PK samples should only be collected from the contralateral arm and not from the drug infusion arm.
- ^b Triplicate ECGs are collected before PK sample collection. See also Section 9.3.12. Triplicate 12-lead ECG measurements are performed using an ECG recorder. Collection of triplicate ECG begins after patient has rested in supine position for approximately 5 minutes. Each ECG recording of the triplicate ECGs occurs within 3 minutes of each other and over a 10-minute window. When the timing of triplicate and single (safety) ECGs coincide, the site can use the triplicate ECG collection for safety evaluation. The ECG data collected on these ECG recorders can also be used as safety ECGs for assessment on site by investigator (ERT will ensure ECG recorders can transmit ECGs for on-site assessment for investigator). On C1D1, patients will abstain from eating food or having anything to drink except water from a minimum of 2 hours before collection of the predose ECGs until after collection of the 1 hour after end of modakafusp alfa infusion triplicate ECGs. A low-calorie and low-sodium light meal is permitted immediately after the 1-hour postinfusion ECG has been collected. Light meals are permissible immediately after collection of the 2-hour and 6-hour postinfusion ECG timepoints. In patients unable to comply with these recommendations, any food intake should be limited to the smallest required portion of bland food.
- ^c Cycle 5 only.
- ^d Cycle 2 only.
- ^e Blood samples for pembrolizumab PK will only be collected at the visits with pembrolizumab dosing (ie, Cycle 1, Cycle 3, Cycle 5, Cycle 7 and beyond).

16.8 Table 16.h Sparse Serum PK Sampling Schedule to Characterize PK of Modakafusp Alfa and Pembrolizumab During Phase 2 Expansion Phase (excluding Safety Lead-In Periods)

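### In phase 2 the Day 1 negative pregnancy result must be in hand only before modakafusp alfa, although pembrolizumab is infused first and may be continued alone

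*Protocol*

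**What the plan says.** Section 9.3.9 contains two separate requirements for patients of childbearing potential. The test itself is due before dosing, within 72 hours, and no drug is named. The result is then required "on Day 1 of each cycle with negative results available before modakafusp alfa is administered". Footnote k of Tables 16.d and 16.e uses the same sentence for phase 2.

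Three other places bear on it:

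- Section 8.1 fixes the order of infusion: "Pembrolizumab will be administered before modakafusp alfa on days when both modakafusp alfa and pembrolizumab are given". Footnote e of the phase 2 schedule adds the spacing: "At least 30 minutes should elapse between the completion of the infusion of the pembrolizumab and the infusion of modakafusp alfa".
- Section 8.6.4 allows the second drug to go on alone: "patients who discontinue modakafusp alfa may continue pembrolizumab as a single agent if pembrolizumab discontinuation criteria are not met".
- Section 4.3.4 attributes pembrolizumab toxicity to "activation of autoreactive T-cells resulting in immune-related adverse events (irAEs) and embryofetal toxicity".

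On the EOT visit, 8.6.4.1 counts 30 to 40 days from the last modakafusp alfa dose. Section 6.3.1 counts 30 (+10) days from the last dose of study drug, the EOT column of Table 16.e counts from the last dose, and 8.6.4 ties the visit to stopping both drugs.

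**The concern.** The sentence in 9.3.9 fits phase 1b, where modakafusp alfa is the only drug. In phase 2 it puts the check after the first infusion of the day. For a patient on pembrolizumab alone, it refers to a dose that is no longer given.

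The drug left out is the one for which the protocol states a fetal risk. Section 8.9.1 describes the effect of modakafusp alfa on pregnancy as unknown. Section 7.1 asks for contraception until 4 months after pembrolizumab, compared with 7 days after modakafusp alfa. If a positive result arrives once pembrolizumab has been infused, that exposure cannot be reversed.

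The EOT wording has the same origin, a modakafusp alfa anchor carried into a two-drug phase. Applied literally to a patient who continues pembrolizumab, it would place the EOT assessments, including the final pregnancy test and immunosafety markers, while treatment is continuing.

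**Working it through.** No sample size, power or event count is involved. The check compares sections and adds up times.

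**1. Is there any result requirement before pembrolizumab after Cycle 1?**

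| Place | What it requires | Covers pembrolizumab? |
|---|---|---|
| 9.3.9 and footnote k, test | Test within 72 hours before dosing, each Day 1 | Yes, for doing the test |
| 9.3.9 and footnote k, result | Negative result before modakafusp alfa | No |
| 8.1, opening | All administration criteria met first | Only if a criterion exists; the only one on the result names modakafusp alfa |
| 8.6.2 | Neutrophils, platelets, recovery from toxicity | Pregnancy not mentioned |
| 8.6.4.2 | Reasons to stop pembrolizumab | Pregnancy not listed |
| 10.4 | Both drugs stopped when pregnancy is found | Yes, but only once it is known |

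Entry is covered: a negative screening test is required, it is repeated at C1D1 if more than 72 hours old, and exclusion criterion 15 bars a positive screening test. What remains is a result still pending when pembrolizumab is due after Cycle 1. On the Q6W schedule the combination days concerned start at Cycle 3.

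**2. How far ahead of modakafusp alfa does pembrolizumab start?**

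Inputs from 8.1: infusion 30 ± 10 minutes, then a gap of at least 30 minutes.

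- Shortest infusion: 20 + 30 = 50 minutes.
- Nominal infusion: 30 + 30 = 60 minutes.

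A result arriving in that interval satisfies 9.3.9 as written.

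**3. EOT windows.**

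Let day 0 be the last modakafusp alfa dose, and let one further pembrolizumab dose fall on day x. Section 8.6.4.1 gives days 30 to 40. Section 6.3.1 gives days x + 30 to x + 40. The two do not overlap when x + 30 > 40, that is, when x > 10.

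- Last modakafusp alfa dose in an even cycle, x = 21: days 51 to 61. Distance from the first window: 51 − 40 = 11 days.
- Last modakafusp alfa dose on a combination day, x = 42: days 72 to 82. Distance: 72 − 40 = 32 days. Here the 8.6.4.1 window closes on day 40, before pembrolizumab is next due on day 42.
- With the ±4-day visit windows of Table 16.e used in opposite directions, x falls by 8 to 13 or 34, leaving 13 + 30 − 40 = 3 days or 34 + 30 − 40 = 24 days.
- With an even-cycle modakafusp alfa dose given 14 days late and pembrolizumab kept on its original date, x = 21 − 14 = 7. The 6.3.1 window becomes days 37 to 47, which overlaps days 30 to 40. The protocol does not say whether pembrolizumab moves with a delayed cycle, so keeping its date is an assumption.

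**The case against.** The best defence of the pregnancy wording is that 8.1 already settles it: "All protocol-specific criteria for administration of study drug must be met and documented before drug administration". That section treats both infusions as study drug, so a careful site would clear all Day 1 checks before the first one. The test must also precede dosing, may be done up to 72 hours ahead, and may be a urine test. Once pregnancy is known, 10.4 says the participant "should be withdrawn and modakafusp alfa, and pembrolizumab if applicable, immediately discontinued", which could also halt an infusion in progress.

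Much of this stands as a reason to expect the problem to be rare. It does not close the gap. The 8.1 sentence enforces criteria stated elsewhere, and the stated criterion for the result names one drug. Section 10.4 cannot act on a result that has not arrived.

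For the EOT visit, the defence is that 8.6.4.1 should be read under its parent 8.6.4, so that a patient still on pembrolizumab has not stopped treatment. Table 16.e and 6.3.1 support that reading, and 9.3 sends the reader to the schedule for timing. This largely stands and makes the EOT item a consistency correction. The sentence in 8.6.4.1 nevertheless counts from modakafusp alfa even after both drugs have stopped.

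Two stronger readings are tempting:

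- A reader might infer that the two EOT windows can never both be met. The delayed-dose case above shows that they can overlap.
- A reader might count Q6W doses over 2 years (weeks 6 to 102, 102 / 6 = 17 after C1D1) and take 17 as the most occasions per patient. That is only the nominal count. Section 6.3.1 allows treatment beyond 2 years with sponsor approval. Sections 6.1.2 and 8.4 allow 200 mg Q3W to be tested in the lead-in, which gives 102 / 3 = 34 doses after C1D1 over the same 104 weeks, starting at Cycle 2.

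**Conclusion.** The point holds as a minor gap in patient-safety wording. In phase 2 nothing in the protocol requires a negative Day 1 result before pembrolizumab after Cycle 1, although pembrolizumab is given 50 minutes or more ahead of the drug that is covered and may be given without it. The gap matters only when the result is still pending at the pembrolizumab infusion. The documents give no basis for a rate, and it is probably low.

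The documents do not support inferring that pregnancy goes untested or that a patient known to be pregnant could stay on pembrolizumab. The predose test and 10.4 rule out both.

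The EOT inconsistency is real but smaller. The 11- and 32-day separations assume nominal dosing and one further pembrolizumab dose. The number of patients continuing pembrolizumab alone is not stated and is probably small. No primary endpoint is affected, and the AE and SAE collection periods in 10.3 run from study drug, so they are unaffected too.

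**What to change.** In 9.3.9 and in footnote k of Tables 16.d and 16.e, require negative results to be available before any study drug (modakafusp alfa or pembrolizumab) is administered. The phase 1b footnote can stay as it is.

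In the same amendment, change 8.6.4.1 so that the EOT visit falls 30 to 40 days after the last dose of the last study drug (modakafusp alfa or pembrolizumab), in line with 6.3.1, 8.6.4 and Table 16.e.

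The cost is a few words, an occasional wait for the result before pembrolizumab, and a later EOT visit than the current 8.6.4.1 wording gives for the few patients who continue on pembrolizumab alone.
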